# **Standard Treatment+ (ST+)**

ST+ is based on clinical practice guidelines[12] and focuses on recognizing and problem solving potential causes of smoking relapse, providing support and reinforcement of success, and encouraging participants to seek support for smoking cessation outside of treatment[13]. When necessary, the counselor discusses strategies for managing relapses to smoking. The elements of the standard smoking cessation content in both interventions is shown in Table 1. In ST+, about 20 minutes of each session are dedicated to teaching progressive muscle relaxation, which is used to match contact time with PPT-S+ while keeping the amount of time focused on smoking in both PPT-S+ and ST+ similar. Relaxation training has not been shown to improve smoking abstinence[12]. Participants are instructed to use relaxation techniques to reduce stress in their day-to-day life as needed.

### PPT-S+

Modeled after our previous pilot [2], the PPT-S+ condition shares the same fundamental smoking cessation components with ST+, but also integrates positive psychology concepts. PPT-S+ focuses on accentuating individuals' strengths (e.g., humor, perseverance, kindness, spirituality) and linking them to behavior change, which is intended to enhance self-efficacy and development of a non-smoker identity, both potential key predictors of immediate and long-term smoking outcomes [8, 14]. PPT-S+ is also gained-framed [15, 16] to highlight that quitting smoking can be a rewarding challenge that enhances mental health [17-19]. Research has shown that positive self-affirmations [20] can reduce defensiveness about health information leading to increased behavioral intentions [21]. Finally, PPT-S+ focuses on increasing attention to the daily experience of positive events, as well as increasing positive social interactions and maintaining PA.

PA is distinct from negative affect both conceptually and empirically [22]. Some studies have suggested that low PA prior to smoking cessation treatment may have a unique association with poor smoking outcomes independent of depressive symptoms [23], although a recent study did not support this conclusion [24]. Both reductions in PA leading up to quit date and low PA after quitting have been implicated in smoking relapse [25, 26]. By focusing specifically on maintaining PA, PPT-S+ seeks to reduce the relative attractiveness of smoking as a mood enhancer and to enhance self-efficacy for remaining abstinent. Prior research has suggested that a behavioral activation approach to increasing positive reinforcement during smoking cessation has promise [27]. The PPT-S+ approach toward increasing positive reinforcement is distinct from that of behavioral activation, but both approaches may operate through similar mechanisms to affect smoking outcomes—providing alternatives for enhancing positive affect other than smoking.

The PPT-S+ model acknowledges that PPT-S+ may directly enhance positive affect, given prior research on positive psychology interventions. It also acknowledges that individuals with greater positive affect may find it easier to engage in PPT-S+ strategies. In our pilot trial, the effect of PPT-S was, in fact, stronger among those with higher levels of positive affect prior to treatment[19]. However, results also suggested that it was use of PPT-S strategies that was more predictive of long-term outcome than positive affect itself.

The following intervention elements are unique to PPT-S+ (see Table 1 for timing of interventions):

PPT-S Model of Smoking Cessation. PPT-S+ highlights that despite initial withdrawal symptoms, quitting smoking results in improved mental health and reduced stress [17, 19, 28-31]. The importance of attending to positive experiences and having positive social interactions when quitting is emphasized, noting that these experiences help people manage future obstacles. Counselors note that the exercises taught in PPT-S+ can be more difficult to complete during periods of stress or low mood, but that regular practice of the exercises has been shown to increase satisfaction with life and positive moods and reduce depression.

Positive Introductions. PPT-S+ begins by introducing the concept of signature strengths and how those can be important in quitting smoking. Participants are provided feedback about their top five signature strengths based on the Values in Actions Survey [32], which assesses 24 signature personality strengths such as *Love of Learning*, *Kindness*, *Appreciation of Beauty*, and *Gratitude*. Participants are asked to share how they have demonstrated use of one of these strengths in a recent situation.

Using Signature Strengths. Counselors highlight the role that signature strengths play in leading an engaged life and handling challenges. Throughout treatment, participants are asked to consider how they can employ their signature strengths to help them manage high-risk situations for smoking. For example, someone with high *Love of Learning* may be encouraged to seek out information on the health benefits of quitting smoking, whereas someone high in *Kindness* may be encouraged to use some of their money saved from not smoking to treat a friend to dinner.

Three Good Things. At session 1, participants are instructed to record by text messaging three good things that happened each day. This exercise has been shown to have rapid and lasting effects on reducing depressive symptoms and increasing happiness [33]. This exercise is continued through session 3, at which point participants can choose whether to continue the exercise over the following weeks.

Savoring. At session 2, counselors introduce the concept of savoring positive experiences, including sensory experiences (e.g., savoring chocolate rather than eating it in one bite), positive memories, and accomplishments. They assign participants to savor at least two experiences each day for two weeks and to record what they savored at the end of each day by text messaging. They continue this exercise through session 4.

Active/Constructive Responding. At session 4, participants are instructed to listen carefully when people they care about report good events. They are instructed to go out of their way to respond actively and constructively to these events and to keep a record of these experiences through daily text messaging.

Savoring Acts of Kindness. This exercise begins at session 5 and asks participants to become aware of when they exhibit kind behavior toward another person (or note others being kind) and to savor the kind behavior by noticing it and writing it down. Participants are asked to text the kind acts they did or witnessed each day. This exercise is based on a prior study showing that writing down one's acts of kindness enhanced well-being [34].

Maintenance Exercise. In the final session, participants discuss their experiences with the PPT-S+ exercises and choose which exercise to continue over the next two weeks.

### **Text Messaging**

Participants in both ST+ and PPT-S+ receive a core set of text messages to support smoking cessation, following the TXT-2-Quit (T2Q) program developed by Bock and colleagues

[35]. The frequency of T2Q messages in PPT-S+ is reduced somewhat to accommodate the PPT-specific texts without creating unequal response burden between study arms. Participants will enroll in the program at baseline by responding to a text message. T2Q is an 8-week core program of daily texts tailored to the user's phase of quitting (e.g., preparing to quit, early weeks of active quitting, sustaining a recent quit, relapsed, preparing to make a second quit attempt). Message content includes behavioral (e.g. "Keep a stress ball handy to squeeze during times of intense craving."), motivational messages (e.g. "You decided to quit smoking and you're doing it. You're awesome") and information on dealing with nicotine dependence and withdrawal (e.g., "The worst of nicotine withdrawal is over in a few weeks, but breaking the smoking habit comes more slowly."). T2Q is flexible, allowing for special messages for each phase of quitting (e.g., recently quit, recently relapsed, maintaining abstinence, etc.) and allowing participants to set a unique quit date.

All participants will set a quit date to coincide with session 3 of counseling, but the program can accommodate those who need to set another quit date. Individuals who relapse are encouraged to make another attempt at cessation, and more intensive messaging is given to those recently quit or relapsed. Participants in ST+ receive 1 message per day leading up to a quit date, 4 messages per day in the 2 weeks immediately after quit date, and 2 messages per day in the four weeks after that. Those in PPT-S+ receive slightly fewer T2Q texts: 1 message per day leading up to a quit date and 2 messages per day in the 4 weeks after their quit date. Additional help is available on demand through automated motivational messages sent in response to a texted key word (e.g., "crave" or "slip") [35].

# **Text Messaging in PPT-S+**

In addition to T2Q messages, participants in PPT-S+ will receive daily texts intended to increase positive cognitions and engagement with exercises and to prompt participants to consider their signature strengths and how these can be used to facilitate quitting. Morning texts provide static messages relevant to a given exercise ("Notice what good things happen in other people's lives. Help them celebrate. It makes you both feel good!"), while afternoon/evening texts are interactive and ask for open-ended descriptions of what participants did to complete that day's exercise ("Did you find at least one chance today to respond actively and with enthusiasm to someone's good news?"), with a reminder sent after one hour if no response is received. These responses are tabulated for the smoking cessation counselor. Text messages specific to an exercise are initiated at the respective counseling session at which that exercise is introduced by texting a key word, e.g., 'Savor,' to initiate the savoring texts. The exercise continues each day following the session until that exercise is replaced by a new exercise. At session 6, participants choose which exercise they want to continue and receive texts based on their choice for an additional two weeks. The texting protocol for PPT-S+ was developed and finalized based on pilot testing done with nine participants prior to initiating the randomized trial.

### Masking/blinding

Participants will be randomized to ST+ or PPT-S+ after completing their baseline assessment by the Project Coordinator, who does not conduct outcome assessments. Due to the timing of the randomization procedures, project staff who conduct the baseline visit will have no way of knowing participants' study condition. Staff conducting follow-up outcome assessments will not be informed of condition assignment.

### 4.9 Timeline

Recruitment began in February 2017 and will continue until approximately April of 2020. Follow-ups will continue throughout this time and will be completed in mid-2021.

AFTER MARCH 2020: Given that recruitment had not yet reached its final goal, we restarted enrollment of new participants in June of 2020 and continue to enroll new participants through September 2020 with all follow-ups completed by December 2021.

# Sample size calculations

We estimated abstinence rates in PPT-S+ by roughly averaging and rounding the abstinence rates seen in our developmental trial [18] and pilot randomized controlled trial [19]. For PPT-S+, we estimated 45%, 30%, and 25% abstinence at 12, 26, and 52 weeks, with 20% continuously abstinent. Results of the pilot study suggested differences in abstinence rates between PPT-S and ST that ranged from roughly 12% to 15% [19]. Therefore, for ST+, we estimated 30%, 17.5%, and 12.5% abstinence at 12, 26, and 52 weeks, with 8% continuously abstinent; such effects would represent a clinically meaningful effect for PPT-S+.

For the analysis of point prevalence abstinence over time, we used a covariance matrix based on our past trial [19] and a program developed for power analysis for generalized estimating equations [36] and determined that a sample size of 272 participants would be needed to achieve power of .80 given our estimated abstinence rates. For the single measure of verified continuous abstinence, 298 participants are needed for power of .80. To allow for up to 10% of participants being lost to follow-up, however, we allowed for an initial sample of 340 in order to ensure adequate statistical power for our analyses.

	Planning for high-risk situations	Signature strengths in quitting smoking
5	Benefits of quitting	3 Good Things (optional)
	Managing smoking 'slips'	Savoring Acts of Kindness
	Nicotine patch review	Signature strengths in quitting smoking
	Planning for high-risk situations	
	Benefits of quitting	Review of PPT-S+ exercises
	Managing smoking 'slips'	Choosing PPT-S+ exercises to continue
	Nicotine patch tapering	
	Planning for high-risk situations	

*Note.* PPT-S+ = positive psychotherapy for smoking cessation plus text messaging

Study Analysis Plan

Positive Psychotherapy for Smoking Cessation Enhanced With Text Messaging: A Randomized

Controlled Trial

NCT02997657

December 22, 2022

[name]., Principal Investigator

Analysis Plan

Initial analyses will use chi-square tests to examine group differences in biochemicallyvalidated, 7-day point prevalence smoking abstinence at each follow-up as well as continuous abstinence across follow-ups. The primary outcome analysis will utilize Generalized Estimating Equations [1, 2] to test the effect of treatment condition on abstinence at 12, 26, and 52 weeks post quit date. GEE is a method of repeated measures analyses for categorical and continuous outcomes that allows for appropriate modeling of covariance structures when observations are correlated across time [3]. The primary, between groups, independent variable in the analysis is treatment group assignment. ST+ will be used as the reference group in this model. The model will contain a linear effect of time as well as the variables included in the urn randomization gender, cigarette dependence, and CES-D PA—following clinical trial analysis recommendations [4]. A second step will test the interaction between treatment condition and time to determine whether relative effects of PPTS+ change over time.

We will also determine if intervention engagement, reduced attraction to smoking, or greater self-efficacy mediates the relationship between PPT-S+ and smoking behavior. A regression analysis will be performed predicting the mediators at session 6 (note that the self-report measures assess strategies used during the quit attempt retrospectively, while attraction and self-efficacy refer to the current moment). Additionally, we will run a second model which adds the mediators to the main effects generalized estimating equations model testing outlined in the previous paragraph. We will use the asymmetric products of coefficients method to calculate the significance of this indirect effect and its 95% confidence interval using the RMediate program [5, 6]. Mediators will be tested sequentially such that strategies will be entered first followed by reduced attraction to smoking and self-efficacy, which serve as more proximal mediators. Follow-up analyses will examine individually each of the four core PPT-S strategies to isolate whether either of these are more important to outcomes.

We will also test whether PA moderates the effect of PPT-S+ on smoking outcome. To do this, we will add to the model testing an interaction term between PA and PPT-S+. Given a significant interaction, follow-up analyses will establish whether there is a crossing point of PA level at which PPT-S+ is not likely to be more effective than ST+. Analyses will be repeated with the CES-D total score as the moderator.

- 1. Zeger, S.L. and K.-Y. Liang, *Longitudinal data analysis for discrete and continuous outcomes*. Biometrics, 1986. **42**: p. 121-130.
- 2. Liang, K.-Y. and S.L. Zeger, *Longitudinal data analysis using generalized linear models*. Biometrika, 1986. **73**(1): p. 13-22.
- 3. Hall, S.M., et al., *Statistical analysis of randomized trials in tobacco treatment: longitudinal designs with dichotomous outcome*. Nicotine Tob Res, 2001. **3**(3): p. 193-202.
- 4. Moher, D., et al., *CONSORT 2010 explanation and elaboration: updated guidelines for reporting parallel group randomised trials.* BMJ, 2010. **340**: p. c869.
- 5. MacKinnon, D.P., et al., *A comparison of methods to test mediation and other intervening variable effects.* Psychol Methods, 2002. 7(1): p. 83-104.
- 6. Tofighi, D. and D.P. MacKinnon, *RMediation: an R package for mediation analysis confidence intervals.* Behav Res Methods, 2011. **43**(3): p. 692-700.

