### **Outcome Variables**

### **Primary outcome measures**

The primary outcome for testing intervention efficacy is biochemically verified 7-day point-prevalence abstinence at 12-, 26-, and 52-week follow-ups. We will also use the Timeline Followback [3, 4] to assess time to first lapse and relapse and continuous abstinence from smoking. Participants will provide breath samples for expired carbon monoxide (CO) analysis at baseline, each treatment session, and each follow-up interview. At 12-, 26-, and 52-week follow ups self-reported smoking abstinence with no other use of nicotine-containing products—including nicotine replacement therapy and electronic cigarettes—will be verified by both CO (cutoff value of  $\leq$ 4ppm) [5] and saliva cotinine radioimmune assay analysis (cutoff value of  $\leq$  15 ng/ml) [6]. For those reporting smoking abstinence, but with past 7-day use of other nicotine containing products, abstinence will be verified only by CO. Continuous smoking abstinence will be defined as self-reporting no cigarettes smoked since quit date with abstinence biochemically confirmed at each follow-up or confirmed by collateral reports from significant others.

AFTER MARCH 2020: Self-reported abstinence was biochemically confirmed with a NicAlert test which was sent to the participants how and self-administered while being observed by the research assistant on Zoom.

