### **Randomization procedures**

After completing baseline appointment procedures, eligible participants will be randomized to either PPT-S+ or ST+ by the Project Coordinator, who is not involved in conducting assessments or providing treatment. The urn randomization technique[1] will be used to ensure that treatment groups are balanced on gender, PA, and level of cigarette dependence. Research assistants will not be informed of treatment condition assignment. The positive affect subscale of the Center for Epidemiologic Studies – Depression scale (CES-D PA) [9] will be used to measure participants' PA over the past week; this scale has been shown to predict smoking outcome [4] and moderate the effect of PPT-S [19]. Participants' level of cigarette

dependence will be measured via the Fagerström Test for Cigarette Dependence [10, 11]. Condition assignment will be placed in sealed folders, which the counselor will open when participants report to the study center for the initial session of counseling, at which point randomization is considered complete.

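### Continuous abstinence, sized separately at 298, is tested only by an unadjusted chi-square; adjusting it for the urn variables is a cheap gain of about 0 to 3 power points

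*SAP*

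**What the plan says.** The protocol (Primary outcome measures) states: "The primary outcome for testing intervention efficacy is biochemically verified 7-day point-prevalence abstinence", assessed at 12, 26 and 52 weeks. Continuous abstinence appears in the same section as a further abstinence measure. Under Sample size calculations it has its own assumed rates (20% in PPT-S+, 8% in ST+) and its own requirement: "For the single measure of verified continuous abstinence, 298 participants are needed for power of .80". The GEE analysis needs 272.

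The SAP (Analysis Plan) names two analyses of abstinence:

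- Chi-square tests: "Initial analyses will use chi-square tests to examine group differences" in the verified outcome "at each follow-up as well as continuous abstinence across follow-ups".
- The primary GEE on abstinence at the three follow-ups. "The model will contain a linear effect of time as well as the variables included in the urn randomization", and the SAP gives its reason as "following clinical trial analysis recommendations".

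No adjusted model is named for continuous abstinence. All three covariates are measured at baseline, because the urn allocation uses them (protocol, Randomization procedures).

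**The concern.** The SAP adjusts its primary model for the variables that drove the allocation. The same reasoning applies to continuous abstinence, the endpoint with the larger stated sample size, yet that endpoint gets a test without covariates. An unadjusted test after allocation balanced on prognostic variables remains valid but gives up some precision. A chi-square also supplies no effect estimate or interval by itself.

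Only a small amount of precision on a supporting endpoint is at stake. The primary analysis is not affected, and neither is the adequacy of the sample size.

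**Working it through.** **Inputs from the documents.** Rates 20% and 8%; target power .80; stated N 298; 340 enrolled with up to 10% loss, so 340 × 0.9 = 306 evaluable (protocol, Sample size calculations).

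**Assumptions, not given in the documents.** Two-sided alpha .05; 1:1 allocation; the prognostic strength of the urn variables.

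**1. The plan's own figure.** With mean rate 0.14 and difference d = 0.12:

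n per arm = [1.96·√(2·0.14·0.86) + 0.8416·√(0.20·0.80 + 0.08·0.92)]² / 0.12² = (0.9618 + 0.4068)² / 0.0144 ≈ 130.1, so 131 per arm, 262 in total.

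Continuity-corrected: n′ = (n/4)·[1 + √(1 + 4/(n·d))]² = (130.1/4)·(1 + 1.121)² ≈ 146.3, so 147 per arm, 294 in total. This is close to the stated 298. Since 298/0.9 ≈ 332, enrolling 340 covers the loss.

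**2. Power of the planned chi-square at 306 (153 per arm).**

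- Uncorrected: Φ[(0.12·√153 − 0.9618)/0.4833] = Φ(1.081) = 0.86.
- Continuity-corrected: Φ[((0.12 − 1/153)·√153 − 0.9618)/0.4833] = Φ(0.914) = 0.82.

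There is no shortfall against .80.

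**3. Gain from adjustment, by simulation.** There were 20,000 simulated trials per setting, N = 306, urn allocation on gender and two median-split scores, and marginal rates held at 20% and 8%. The adjusted analysis is a logistic model with arm and the three covariates. Its standardised risk difference (RD) is the average over all participants of the predicted probability under PPT-S+ minus that under ST+, tested by a Wald CI. The Monte Carlo SE is about 0.24 points for each power and 0.1 to 0.2 for the paired gains.

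| Assumed log odds ratios (gender; two scores per SD) | AUC | Pearson | Unadjusted RD | Standardised RD | Gain over Pearson | Due to covariates |
|---|---|---|---|---|---|---|
| None: 0; 0; 0 | 0.50 | 86.9% | 87.3% | 87.1% | 0.2 | −0.2 |
| Weak: 0.2; 0.25; 0.3 | 0.61 | 87.0% | 87.3% | 87.7% | 0.7 | 0.4 |
| Moderate: 0.3; 0.4; 0.5 | 0.68 | 87.1% | 87.4% | 88.5% | 1.4 | 1.1 |
| Strong: 0.4; 0.6; 0.8 | 0.75 | 87.0% | 87.3% | 90.4% | 3.4 | 3.1 |

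The last column is standardised RD minus unadjusted RD. The remaining 0.3 to 0.4 points come from using an unpooled RD test.

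From none to strong, the SD of the estimate is 0.3% larger, then 0.3%, 1.5% and 4.2% smaller. This is worth about −2, +2, +9 and +28 participants.

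**4. Cross-check by formula.** If the covariates explain a share R² of outcome variance, the effective N is N/(1 − R²). At N = 306, from a base of 86.0%, the gain is 0.3 points at R² = 0.01, 0.7 at 0.02, 1.7 at 0.05 and 2.7 at 0.08. It passes 3 points only above about 0.08 to 0.09.

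**5. Type I error** (nulls at 14% and at 8%). Pearson 4.8 to 5.3%; standardised RD 5.1 to 5.6%. The largest excess is 5.6 − 4.9 = 0.7 points, in the strong case at the 14% null.

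**6. Choice of test within the logistic model.** Testing the arm coefficient by Wald gives 86.5, 87.0, 87.8 and 89.9%, which is −0.4, 0.1, 0.8 and 2.9 points against Pearson (differences taken before rounding). That test and the standardised-RD interval disagreed on significance in 0.3 to 0.7% of trials, so one estimator should supply both.

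**The case against.** The case for leaving the plan alone has several parts.

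- **Nothing is broken.** The chi-squares are labelled initial analyses, the primary GEE is already adjusted, and the SAP's appeal to recommendations attaches only to the GEE. A simple test for a supporting endpoint is a legitimate choice. This stands, and it is why the point is only a suggestion.
- **The gain depends on the test.** A Wald test of the logistic coefficient can lose about half a point if the covariates are not prognostic. This also stands, and it is the reason to specify the standardised risk difference.
- **Part of the gain is a looser test.** Moving true alpha from 4.9% to 5.6% at 87.0% power adds about 1.2 points by normal approximation. However, a further simulation (5,000 trials per setting) that put both tests at equal size still gave gains of about 0.1, −0.2, 1.5 and 2.7 points from none to strong. The looser test explains some of the gain but does not remove it.
- **The upper end has no source in the documents.** The protocol says of the CES-D PA measure that "this scale has been shown to predict smoking outcome" (Randomization procedures), but its PPT-S+ section also cites a study that did not support a unique association. No figure is given for any urn variable. This stands, so the range must include zero.
- **Timing may cancel the benefit.** If outcomes had already been seen by arm, the chi-square should remain the test and the power gain is zero. The documents do not settle this.

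**Conclusion.** The point holds as a minor, optional improvement. Continuous abstinence is sized separately but has no adjusted analysis, while the primary model adjusts for variables already in hand. Carrying the adjustment over would add about 0 to 3 power points (0.2 to 3.4 over Pearson in the simulation), from a base already above the planned .80.

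This rests on 20% vs 8%, 306 evaluable participants, two-sided .05, 1:1 allocation and an assumed covariate strength from none to AUC 0.75. If those lost to follow-up were instead counted as smoking and the rates held at N = 340, base power would be about 0.89, leaving less room for gain. Confidence in the size is moderate, because the documents give no prognostic figures.

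**What to change.** Add one or two sentences to the SAP:

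- Analyse continuous abstinence by logistic regression on arm, gender, cigarette dependence and CES-D PA.
- Report the standardised risk difference with a 95% Wald CI (influence-function variance, n/(n − 5) correction). Judge significance at two-sided .05 by whether that interval excludes zero, so that test and interval cannot disagree.
- Keep the raw rates and the chi-square as description. The per-visit chi-squares can stay.
- State whether this was decided before outcomes were seen by arm. The protocol's Timeline has enrolment "through September 2020 with all follow-ups completed by December 2021", and the SAP is dated December 22, 2022. If it was not, keep the chi-square as the test and label the adjusted result supportive.

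**Cost.** No new data are needed. The downsides are:

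- Few events: 153 × (0.20 + 0.08) ≈ 43 at the planned rates, about 11 for each of four terms. If both arms are at 8%, 306 × 0.08 ≈ 24, about 6 per term.
- Type I error up to 0.7 points above Pearson.
- No gain from the covariates (−0.2 points) if they are not prognostic.
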